# Design of the pilot, proof of concept REMOTE-COVID trial: REmote MOniToring usE in suspected cases of COVID-19 (SARS-CoV 2)

## A trial protocol

[name]1\*, [name], [name], [name], [name], [name]

- 1) Division of Surgery & Cancer, [name]
- 2) West Middlesex University Hospital, [name]

Clinical trials registration information: ClinicalTrials.gov Identifier: NCT04337489

16 March 2020

16 Abstract:

17 Background: The outbreak of SARS-CoV-2 (coronavirus, COVID-19), declared a pandemic by the  
18 World Health Organisation (WHO) is global health problem with ever-increasing attributed deaths.  
19 Vital sign trends are routinely used to monitor patients with changes in these parameters often  
20 preceding an adverse event. Wearable sensors can measure vital signs continuously (e.g. heart rate,  
21 respiratory rate, temperature) remotely and can be utilised to recognise early clinical deterioration.

22 Methods: We describe the protocol for a pilot, proof-of-concept, observational study to be  
23 conducted in an engineered hotel near London airports, United Kingdom. The study is set to  
24 continue for the duration of the pandemic. Individuals arriving to London with mild symptoms  
25 suggestive of COVID-19 or returning from high risk areas requiring quarantine, as recommended by  
26 Public Health England, or healthcare professionals with symptoms suggestive of COVID-19 unable to  
27 isolate at home will be eligible for a wearable patch to be applied for the duration of their stay.  
28 Notifications will be generated should deterioration be detected through the sensor and displayed  
29 on a central monitoring hub viewed by nursing staff, allowing for trend deterioration to be noted.  
30 The primary objective is to determine the feasibility of remote monitoring systems in detecting  
31 clinical deterioration for quarantined individuals in a hotel.

32 Discussion: This trial should prove the feasibility of a rapidly implemented model of healthcare  
33 delivery through remote monitoring during a global pandemic at a hotel, acting as an extension to a  
34 healthcare trust. Potential benefits would include reducing infection risk of COVID-19 to healthcare  

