35 staff, with earlier recognition of clinical deterioration through ambulatory, continuous, remote  
36 monitoring using a discrete wearable sensor. We hope our results can power future, robust future  
37 randomised trials.

38 Trial registration: ClinicalTrials.gov Identifier: NCT04337489

39 Keywords: remote sensing technology; protocol; clinical trial; patient deterioration; monitoring,  
40 ambulatory.

41 Background:  
42 The recent outbreak of SARS-CoV-2 (COVID-19), declared a pandemic by the World Health  
43 Organisation (WHO) and a growing global health problem, has stretched resources, creating  
44 pressures within the National Health Service (NHS) with implications for patient safety. UK Chief  
45 Medical Officers have raised the risk to the UK to high, with ever increasing confirmed cases and  
46 attributed deaths.

47 High risk travellers with suspected or confirmed cases of COVID-19 are likely to transferred  
48 immediately to hospital. However, travellers with milder symptoms or returning from high risk  
49 areas, a two-week period of observation/quarantine may be required, in accordance with Public  
50 Health England recommendations. The rate of clinical deterioration for individuals suffering with  
51 COVID-19 remains unknown; given that widespread vaccine deployment remains imminently  
52 unforeseeable, novel strategies are required in approaching this pandemic.

53 Vital signs trends (heart rate, respiratory rate, blood pressure, temperature, oxygen saturations) are  
54 routinely used for monitoring hospital patients. Clinical deterioration may be recognised through  
55 changes in these parameters, and often precedes an adverse event. As such, The National  
56 Institute for Health and Care Excellence (NICE) and the Royal College of Physicians (RCP) recommend  
57 that all patients have their vital signs recorded every 12h as a minimum.

58 Across the National Health Service (NHS), the use of the National Early Warning Score 2 (NEWS), a  
59 'track and trigger' warning score, has been implemented in accordance with the RCP to guide on  
60 escalation protocols and monitoring frequency of vital signs. Accordingly, heart rate (HR),  
61 respiratory rate (RR), temperature, blood pressure, oxygen saturations, and level of consciousness  
62 are assessed every 4-6 hours with more frequent monitoring for acutely unwell patients.

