115 data backup policies, ensuring data access and servers are secured.

116 In line with the principles of Good Clinical Practice guidelines, data will be securely archived for a  
117 minimum of 5 years.

118 Following the completion of quarantine, participants will be invited to share their experiences  
119 through using semi-structured interviews and questionnaires. Individual interviews allow for  
120 anonymity and truthful perceptions/attitudes. This method enables narratives to be elicited through  
121 guided but open questioning.

122 *Hypotheses:*

123 1) Continuous remote monitoring with wearable sensors of vital signs will identify  
124 deteriorating patients.  
125 2) Healthcare provision in a hotel will be feasible and acceptable amongst healthcare staff  
126 and participants.

127 *Sequence of events:*

128 Patching patients and using data for academic research

129 1. Eligible participants from the airport will be transferred to the hotel by paramedics.  
130 2. Upon arrival to the engineered hotel, an initial assessment of all participants will be  
131 undertaken. A study information sheet will be provided, and informed consent taken for  
132 wearable sensors to be applied, allowing remote monitoring of vital signs. To ensure  
133 appropriate quarantine.  
134 3. In a designated area within the building, a central monitoring hub will be set up to monitor  
135 the recorded parameters by National Health Service (NHS) healthcare staff from a local  
136 Trust. The hub contains a site manager, porters, security staff, nurses, ambulance services,  
137 professional cleaners, and hotel staff.

138 4. If a participant deteriorates, an alert should be generated on a smartphone device/desktop  
139 computer; following this, an escalation protocol will be trialled to action the alert in an  
140 appropriate manner; hospitalisation may be necessary. Initially, nursing staff will gather  
141 more information through telephone review. Following this, a virtual GP can be contacted  
142 for further advice. Ambulance services and paramedics will be on-site to facilitate  
143 hospitalisation should rapid deterioration occur. These healthcare professionals are  
144 independent and can provide oversight.

145 5. Participants will be invited for an interview and be asked to complete a survey on their  
146 experiences following quarantine completion.

147 6. Participant care records will be stored on an online Care Information Exchange system  

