148 (compliant with General Data Protection Regulation) that is currently in place across the  
149 trust. Electronic health records and patient notes will be reviewed to determine clinically  
150 relevant events if transfer to hospital occurs (e.g. hospital length of stay, mortality,  
151 escalation to ITU).

152 7. Sensor data will be extracted from the central servers containing sensor data for appropriate  
153 statistical analyses for associated clinical efficacy of health outcomes in COVID-19.

154

155 Semi-structured interviews/Questionnaires (mixed methods)

156 1. All participants alongside healthcare staff will be invited to take part in semi-structured  
157 interviews and be given questionnaires. These will take place by the primary lead researcher  
158 using prepared topic guides.

159 2. Written consent will be obtained from those who agree to participate.

160 3. An audio recording will be made of the interviews. Notes reflecting verbal responses may be  
161 taken. The interviews will be conducted at the engineered hotel.

162 4. The recordings will be transcribed, and the data will undergo thematic analyses.

5. Validated and unvalidated questionnaires will also be given enquiring about experiences (e.g. PHQ-9, GAD-7, satisfaction, anxiety related to the devices).

165

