## 166 *Outcomes and progression criteria:*

## 167 Feasibility outcomes:

1. Rate of participation  
Using the confidence interval approach, for a minimum sample size of 10 individuals, we estimate a rate of participation of 90% with a 95% confidence interval of +/- 18%.
2. Generation of an alert following abnormal vital signs (e.g. raised temperature).  
We aim for a minimum of 5 vital alerts to be generated to demonstrate feasibility.
3. Missing data recorded from sensor limited to less than 20% attrition will be a criterion for progression.
4. Number of adverse events relating to the sensor system (e.g., skin reaction to sensor preventing trial continuation)

178 Exploratory clinical outcomes:

1. Actions following alert generation (e.g., phone consultation, virtual general practitioner review, transfer to hospital).
2. Acceptability and usability of the SensiumVitals™ system by healthcare staff and participants (mixed methods analysis)

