## 198 Exclusion Criteria

- Any participants that withdraw their consent.
- A skin condition/reaction preventing wearing the wearable sensor (these can be communicated by the participant to the researcher or healthcare staff at the hotel).
- The presence of a permanent pacemaker or cardiac defibrillator.
- Any form of psychiatric disorder or a condition that, in the opinion of the investigator, may hinder communication with the research team.
- Inability to cooperate or communicate with the research team.

209 Descriptive statistics will be obtained about the baseline characteristics of participants. Continuous  
210 variables will be presented as mean  $\pm$  standard deviation or medians and ranges, depending on  
211 distribution. Categorical variables will be reported as numbers and percentages. The total  
212 frequencies of alerts, proportion of actioned alerts, and resultant actions will be described.  
213 Outcome measures (e.g. phone consultation, virtual GP review, transfer to hospital) will be reviewed  
214 from case notes should escalation occur and described in absolute frequencies. Questionnaire data  
215 will be presented using frequency distributions. Data will be analysed using SPSS, Stata, and  
216 GraphPad.

217 Qualitative analyses:

218 Semi structured interviews will take place by the primary lead researcher using the prepared topic  
219 guides. An audio recording will be made of all interviews. The interviewer may also take field notes  
220 reflecting the verbal responses and reflections to be used to adapt the topic/study direction. The  
221 audio recordings will be transcribed. The data will be analysed appropriately using thematic analysis.

222 To ensure confidentiality and anonymity, each interview will be allocated a pseudonym, to be  
223 applied to the corresponding consent form, topic guide form/field notes and audio file. Their name  
224 will not be included in the audio recording; the pseudonym will be used.

225 Summaries of interview field notes will be typed into a word processor. All paper and soft copies of  
226 field notes, audio files and consent forms will be kept securely in a locker within a locked office and  
227 if in digital format, on a password protected computer and backed up regularly. Information will only  
228 be shared within the study team.

229 Audio recordings will be professionally transcribed verbatim, and a random selection of transcripts  

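### Outcome records are opened only after transfer or escalation and to no fixed day, so later admissions and deaths are not systematically captured and deteriorations without an alert cannot be fully counted

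*Combined protocol and SAP*

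**What the plan says.** Two passages govern when outcomes are looked up, and both are conditional.

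- Sequence of events, step 6: records and notes are examined for clinically "relevant events if transfer to hospital occurs (e.g. hospital length of stay, mortality", ITU escalation). The trigger is transfer.
- The descriptive-statistics paragraph after the Exclusion Criteria: outcome measures such as a phone consultation, a virtual GP review or a transfer are taken "from case notes should escalation occur and described in absolute frequencies". The trigger is escalation.

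The exploratory clinical outcome in Outcomes and progression criteria follows the same logic: "Actions following alert generation (e.g., phone consultation, virtual general practitioner review, transfer to hospital").

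The observation period is the hotel stay. The Abstract says that healthcare professionals unable to "isolate at home will be eligible for a wearable patch to be applied for the duration of their stay", and the same applies to travellers. The length of stay is not fixed. The Background says only that for travellers with milder symptoms or from high-risk "areas, a two-week period of observation/quarantine may be required, in accordance with Public" Health England advice.

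After quarantine, step 5 is the only planned contact: "Participants will be invited for an interview and be asked to complete a survey on their" experiences. The Exclusion Criteria list "Any participants that withdraw their consent" and a skin reaction that prevents wear, with no rule on follow-up once the sensor is off.

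**The concern.** Hypothesis 1 is that monitoring will pick out the people who deteriorate. Step 7 plans to analyse sensor data against health outcomes. The Discussion expects to learn whether vital-sign trends can detect deterioration that needs a hospital bed, and hopes the results will help to power later randomised trials. Each of these needs outcomes for the people the system did not act on as well as for those it did.

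Under the plan, outcome status is verified mainly in people already transferred or escalated. This is partial verification: the number of known deteriorations is a lower bound, collected over stays of unequal length. The Background calls the deterioration rate unknown, and Power considerations says that data for a power calculation do not exist. An event count obtained in this way would be a weak input for a later trial.

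**Working it through.** **The plan's own figure.** The only sample-size figure is a 95% interval of ±18% around 90% participation with 10 people. The Wald half-width is 1.96 × √(0.9 × 0.1 / 10) = 0.186, which agrees with the stated value apart from rounding. The present point does not depend on it; it supplies only the minimum of 10 used below.

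**Who is looked up.** Reading the two triggers against the possible courses gives:

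| Course | Hospital records (step 6) | Case notes (analysis paragraph) |
|---|---|---|
| Alert, then transfer | Yes | Yes |
| Transfer with no prior alert | Yes | Yes |
| Sensor off, still in the hotel, transferred | Yes on the wording, which does not require wear | Yes |
| Escalated to phone or GP review only | No | Yes, with no end day stated |
| Not escalated, leaves the hotel, later admitted or dies | No | No |
| Consent withdrawn | No rule given | No rule given |

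**What is counted.** Write the deteriorations to hospital level as D = a + b + c, where

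- a = those transferred or escalated during the stay,
- b = those arising during the stay but not acted on,
- c = those arising after the stay.

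The plan observes a, and within a it can separate cases with and without a prior alert. It has no systematic route to b or c. For the performance of the sensor the missing quantity is b. For the clinical course and event rate it is b + c.

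**Illustrative size.** The documents give no rate of later admission or death, so q, the risk of such an event per participant, is assumed. The chance of at least one in n participants is 1 − (1 − q)^n.

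| Assumed q | n = 10 | n = 20 | n = 50 |
|---|---|---|---|
| 2% | 18% | 33% | 64% |
| 5% | 40% | 64% | 92% |
| 10% | 65% | 88% | 99.5% |
| 20% | 89% | 99% | about 100% |

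At n = 10 and q = 10% the expected number is 10 × 0.10 = 1, so one uncaptured event can be a large part of all there is to learn. If 10 is the number approached, enrolment at 90% is 9, and the 10% entry becomes 1 − 0.9^9 = 61%.

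**What a full check would give.** If all 10 were traced and none had an uncaptured event, the exact two-sided 95% upper limit would be 1 − 0.025^(1/10) = 30.8% (16.8% for n = 20, 7.1% for n = 50). The check makes the count complete among those traced. It does not make it precise.

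**The case against.** The strongest reply is about purpose. This is a feasibility pilot. Overall design tests feasibility by participation and number of alerts, and the listed outcomes include neither admission nor death. No progression decision changes if a late admission goes unrecorded. That stands, and it limits the weight of the point. It does not remove it, because hypothesis 1, step 7 and the Discussion go beyond those criteria.

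Three stronger readings are tempting, and the documents do not support them.

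- A reader might infer that every deterioration the sensor misses goes unrecorded. Step 6 is triggered by transfer, not by an alert, and Overall design gives the decision to escalate to a senior nurse or GP. A transfer without an alert would be reviewed, and people escalated only to a phone or GP review have their case notes read.
- A reader might infer that anyone who stops wearing the sensor is lost. The transfer trigger does not require wear. The text is silent on follow-up after withdrawal, and silence does not establish that such people are dropped.
- A reader might set an apparent detection rate against a lower true one. The plan does not say that it will report sensitivity, and a person who has left the hotel is no longer monitored, so a later admission is not a failure of the sensor.

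The reply also notes that a look-up in the trust's system will miss admissions elsewhere, and that airport arrivals are a main recruitment group. That is a fair limit on the remedy, and it belongs in its cost. Finally, an interview might reveal a late admission by chance, but interviews are by invitation, held at the hotel and aimed at experience, so they are not a means of ascertainment.

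**Conclusion.** The point holds as a gap in ascertainment. Record review depends on transfer or escalation, has no fixed day, and does not extend to all participants. Admissions and deaths outside those triggers, chiefly after the stay, are not systematically captured. Deteriorations without a preceding alert therefore cannot be fully counted, and hypothesis 1 and the step 7 analysis rest on selectively verified cases.

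The participation, alert-count and missing-data criteria are unaffected. No bias figure can be given, because the documents state neither an event rate nor a detection measure. The probabilities above rest on assumed risks, on independence between participants, and on the minimum of 10 (with 20 and 50 for comparison). The change is worth making because it is cheap, not because the feasibility conclusion is at risk.

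**What to change.** Change step 6 so that the records of every consented participant, transferred or not, are reviewed once for admission, ITU care and death at a fixed day counted from sensor fitting. The investigators should state the day in advance. To capture events after departure, it must lie beyond the expected stay. Align the descriptive-statistics paragraph with this.

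Class each event as (i) during monitored wear, (ii) during the stay without the sensor, or (iii) after the stay, and report the three separately, so that post-stay events are not counted against the sensor. State whether records are still reviewed after the sensor is removed, and what happens on withdrawal of consent. Report the number of participants whose records could not be traced.

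The cost is one look-up per participant in a system the trust already uses, and a line in the consent form. Tracing will be incomplete for travellers whose records lie outside the trust. One follow-up question on hospital attendance would help, but it needs contact details, and the plan has only email addresses given voluntarily for receiving results. A deterioration that resolved without admission would still not be found by this check, and the report should say so. The change concerns research data only and alters no clinical care.

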230 will be checked against recordings for accuracy. Interview transcripts will be analysed using Braun  
231 and Clarke's thematic analysis by two independent researchers; disagreements will be resolved  
232 through discussion. Power considerations:

233 As a pilot study in an unknown viral pandemic, the progression of which is not well established, this  
234 study will appraise the feasibility for hotel remote sensing under these circumstances. Sufficient  
235 other data do not exist to allow for power calculations.

236

237 *Patient and public involvement:*

238 Due to the nature of the pandemic and the current climate (national lockdown advised from the  
239 government) with COVID-19, patient and public involvement was not undertaken for this

240 observational trial. All eligible participants will be approached to enter the study and all recruited  
241 participants can provide email addresses should they wish for dissemination of results.

242 Discussion:

243 To the best of our knowledge, this is the first remote monitoring study focussing on healthcare  
244 delivery during a global pandemic at a remote site (i.e. hotel), acting as an extension to a healthcare  
245 trust. Apart from reducing infection risk to healthcare staff, continuous remote monitoring using a  
246 discrete wearable sensor has the potential to detect earlier clinical deterioration allowing for earlier  
247 intervention and provide further insight into the clinical course of COVID-19 in regards to vital signs.

248 Our pilot study design will test the viability of using a remote site for healthcare delivery during  
249 times of crisis. Continuous vital sign monitoring should provide insight to determine whether vital  
250 sign trends can detect clinical deterioration for COVID-19, requiring hospitalisation. Furthermore,  
251 questionnaires and semi-structured interviews of participants will provide insight into wider  
252 implementation of this technology and provide feedback for improvements. Similarly, semi-  
253 structured interviews of staff will provide a healthcare perspective, particularly thoughts on reducing  
254 potential infection risk through remote monitoring services.

255 Despite the strengths of our study, the design presents inherent limitations. Mainly, the lack of  
256 randomisation and control arm to compare remote monitoring services to 'standard care'.

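### The interviews are described as anonymous but are only confidential and pseudonymised, which leaves acceptability open to favourable answers, a risk the limitations do not mention

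*Combined protocol and SAP*

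**What the plan says.** In Methods, the last paragraph of Wearable sensor system gives the reason for interviewing people individually: it allows for "anonymity and truthful perceptions/attitudes". The timing for participants is in the same paragraph: "Following the completion of quarantine, participants will be invited to share their experiences".

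Under Semi-structured interviews/Questionnaires (mixed methods), item 1 covers both participants and healthcare staff: "interviews and be given questionnaires. These will take place by the primary lead researcher". Item 2 requires written consent. Item 3 provides for audio recording and fixes the place: "taken. The interviews will be conducted at the engineered hotel". Item 5 lists the questionnaires, including satisfaction and device-related anxiety, but not how they are returned.

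Qualitative analyses names the same interviewer again and then states the safeguard: "To ensure confidentiality and anonymity, each interview will be allocated a pseudonym, to be" "applied to the corresponding consent form, topic guide form/field notes and audio file". Names are kept off the recording. One sentence covers the storage of field notes, audio files and consent forms: a locker in a locked office, or a password-protected computer for digital material. Sharing is limited to the study team. Transcripts are made professionally, spot-checked, and go to "thematic analysis by two independent researchers".

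Acceptability appears in hypothesis 2 and as exploratory outcome 2 under Outcomes and progression criteria, to be assessed by mixed methods. No threshold is attached to it.

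**The concern.** Anonymity is offered as a reason to trust the answers, but the procedure does not provide it. A person who speaks face to face with the lead researcher is known to that researcher. A pseudonym that also appears on a written consent form can be traced to the signatory.

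This matters because these answers are the evidence for acceptability. When people tell the person leading a study what they think of the arrangement being studied, criticism may be softened. A reader who accepts the anonymity claim would discount that possibility, and the Discussion would not alert them to it. Softened answers cannot be repaired in the analysis, so the point has to be settled before interviews begin.

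**Working it through.** The plan gives no figure on this point, and no sample size, rate or power calculation bears on it. The check is a comparison of the text.

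**1. Anonymity towards the interviewer.** Wearable sensor system claims anonymity for individual interviews. Semi-structured interviews/Questionnaires (item 1) and Qualitative analyses both assign the interviews to the lead researcher, and item 3 places them at the study hotel. The respondent is not anonymous to the interviewer.

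**2. Anonymity of the records.** Qualitative analyses gives anonymity as a purpose of the pseudonym, then puts that pseudonym on the consent form, the topic guide or field notes, and the audio file. Item 2 makes the consent written. The form itself is not in the documents; I assume that, as usual, it identifies its signatory. The form then acts as the key from name to notes and recording. The storage sentence does not require consent forms to be kept apart from the other records. The data are pseudonymised.

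**3. What each safeguard does.**

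| Safeguard | Protects confidentiality | Bears on what respondents say to the interviewer |
|---|---|---|
| Name kept off the audio, locked or password-protected storage, sharing within the team | Yes | Partly; the interviewer still knows who is speaking |
| Participants interviewed after quarantine | No | Possibly, for participants; no timing is given for staff |
| Professional transcription with spot checks | No | No; protects accuracy |
| Two researchers coding | No | No; protects the analysis |
| Questionnaires as a second source | Not stated | Could help, but neither return route nor anonymity is specified |

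In item 1 the sentence naming the lead researcher directly follows the mention of both interviews and questionnaires. The text therefore leaves open whether the questionnaires also pass through that person.

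**4. What the limitations cover.** The Discussion names one source of favourable reporting: healthcare professionals' familiarity with physiological monitoring. It does not mention the interviewer or the setting.

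**5. Consequence for decisions.** Overall design tests feasibility by participation rate and number of alerts. Under Outcomes and progression criteria, the missing-data limit is also a progression criterion. Acceptability is exploratory, so no go or no-go decision depends on it, although it is half of hypothesis 2.

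**6. Size.** The documents give no favourable-response rate, no acceptability threshold and no interviewer effect. Neither the existence nor the size of a bias can be derived from them.

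**The case against.** The best defence is that the claim can be read narrowly: individual interviews give privacy from other respondents, as group interviews would not. The confidentiality measures are real, and participants are interviewed once quarantine is over. This stands in part. It softens the first use of the word, but not the second, where anonymity is a stated purpose of a pseudonym that is then written on the consent form.

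Several stronger readings are tempting, and the documents do not support them:

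- **That acceptability is biased favourably.** Nothing in the documents shows this. They support a risk, plausibly in the favourable direction.
- **That the pseudonym on the consent form makes answers more favourable.** It does not. It is a linkage and confidentiality matter. The risk of softened answers comes from who asks and where.
- **That there are no safeguards.** There are several, as tabulated; they provide confidentiality rather than anonymity.
- **That respondents are judging the lead researcher's own product or care.** The sensor is a commercial system, no competing interests are declared, and monitoring is done by NHS staff. The documents do not say that the lead researcher provides care or manages the staff interviewed.
- **That the bias amounts to some number of percentage points.** With ten respondents one changed answer moves a proportion by 1/10, or 10 points, but that is only the coarseness of a small sample. Ten is the minimum used for the participation-rate estimate. The number of staff respondents is not stated, and the plan defines no percentage-acceptable endpoint.
- **That one of the two coders should do the interviews.** The text does not show that either coder is separate from the lead researcher or available to interview; independent may mean only independent of each other. It would also give up a coder who had not met the respondents.

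**Conclusion.** The point holds in a limited form. The interviews are confidential and pseudonymised, not anonymous, and the protocol should not present them as anonymous or rest truthfulness on that. Interviewing by the lead researcher at the study site leaves acceptability open to favourable answers of unknown size, and the limitations omit this.

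The conclusion assumes only that a written consent form identifies the person who signs it. The consequence is modest: an exploratory outcome without a threshold is affected, and the participation, alert and missing-data criteria are not. It still merits a change, because acceptability carries part of hypothesis 2 and the correction costs almost nothing if made before interviews start.

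**What to change.** 1. Have participants and staff complete the already planned acceptability and satisfaction questionnaire themselves, under a study number, before the interview. Specify a return route other than the lead researcher. Base the reported acceptability frequencies on it; the plan already presents questionnaire data as frequency distributions. The interviews then supply explanation and themes.
2. Keep the pseudonym off the consent form. Hold a separate link list, stored apart from the notes and audio files. This does not make the data anonymous, but the consent form no longer serves as the key.
3. In Wearable sensor system and Qualitative analyses, describe the interviews as confidential and pseudonymised instead of anonymous. Add to the limitations in the Discussion that interviewing by the lead researcher at the study site may draw favourable answers.

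The cost is slightly more handling of forms and one link list. Recruitment, sensors, monitoring and the choice of interviewer are unchanged. Because the interviewer stays the same, the risk remains for the interview themes; the third change makes it visible to the reader.
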